 *Dept. of Veterans Affairs, West Haven VA HSS Approval Date:
 *Radioactive Drug Research Committee (RDRC) Approval Date:
 YNHH-Radiation Safety Committee (YNHH-RSC) Approval Date:
 Magnetic Resonance Research Center PRC (MRRC-PRC) Approval Date:
 YSM/YNHH Cancer Data Repository (CaDR) Approval Date:
 Dept. of Lab Medicine request for services or specimens form

***Approval from these committees is required before final HIC approval is granted. See instructions for documents required for initial submission and approval of the protocol. Allow sufficient time for these requests. Check with the oversight body for their time requirements.**

2. **Probable Duration of Project:** State the expected duration of the project, including all follow-up and data analysis activities. 3-4 years.

3. **Targeted Enrollment:** What is the number of subjects

a. targeted for enrollment at Yale for this protocol? If this is a multi-site study, what is the total number of subjects targeted across all sites? Approximately 40 subjects all from Yale.

b. expected to sign the consent form? 40 subjects

c. expected to complete some or all interventions for this protocol? 40 subjects

4. Research Type/Phase: (Check all that apply)**a. Study Type**

Single Center Study

Multi-Center Study

Does the Yale PI serve as the PI of the multi-site study? Yes No

Coordinating Center/Data Management

Other:

b. Study Phase N/A

Pilot

Phase I

Phase II

Phase III

Phase IV

Other (*Specify*)

c. Area of Research: (Check all that apply) Note that these are overlapping definitions and more

version

than one category may apply to your research protocol. Definitions for the following can be found in the instructions section 4c:

- | | |
|---|--|
|  Clinical Research: Patient-Oriented |  Clinical Research: Outcomes and Health Services |
|  Clinical Research: Epidemiologic and Behavioral |  Interdisciplinary Research |
|  Translational Research #1 (“Bench-to-Bedside”) |  Community-Based Research |
|  Translational Research #2 (“Bedside-to-Community”) | |

5. Is this study required to be registered in a public database? Yes No

If yes, where is it registered?

Clinical Trials.gov registry

Other (*Specify*)

6. Will this research study utilize clinical care services at Yale New Haven Hospital or YMG?

Yes No

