Do you know of any real or apparent institutional conflict of interest (e.g., Yale ownership of a sponsoring company, patents, licensure) associated with this research project?

- Yes (provide a description of that interest in a separate letter addressed to the HIC.)
 No

As Chair, do you have any real or apparent protocol-specific conflict of interest between yourself and the sponsor of the research project, or its competitor or any interest in any intervention and/or method tested in the project that might compromise this research project?

- Yes, and I agree to submit the Protocol-Specific Conflict of Interest Disclosure Form.
 No

I assure the HIC that the principal investigator and all members of the research team are qualified by education, training, licensure and/or experience to assume participation in the conduct of this research trial. I also assure that the principal investigator has departmental support and sufficient resources to conduct this trial appropriately.

 Chair Name (PRINT) and Signature

 Date

 Department

YNHH Human Subjects Protection Administrator Assurance Statement

Required when the study is conducted solely at YNHH by YNHH health care providers.

As Human Subject Protection Administrator (HSPA) for YNHH, I certify that:

- I have read a copy of the protocol and approve it being conducted at YNHH.
- I agree to submit a Protocol-Specific Conflict of Interest Disclosure Form if I am aware of any real or apparent institutional conflict of interest.
- The principal investigator of this study is qualified to serve as P.I. and had the support of the hospital for this research project.

 YNHH HSPA Name (PRINT) and Signature

 Date

For HIC Use Only

Date Approved

Human Investigation Committee Signature

SECTION V: RESEARCH PLAN

1. **Statement of Purpose:** State the scientific aim(s) of the study, or the hypotheses to be tested.
The aim of the study is to determine if N-acetylcysteine is an effective treatment for OCD in children.
2. **Background:** Describe the background information that led to the plan for this project. Provide references to support the expectation of obtaining useful scientific data.

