NAC is a naturally occurring amino-acid that has been used safely for decades as an antioxidant agent and as an antidote for acetaminophen overdose. Due to its benign safety profile, NAC is available as an over-the-counter medication at a cost of less than 25 cents a day. More recently, NAC has been demonstrated to be a glutamate modulating agent. NAC is converted to cystine, a substrate for the glutamate/cystine antiporter located on glial cells. The uptake of cystine by glia causes glial release of glutamate into the extrasynaptic space, where it appears to stimulate inhibitory metabotropic glutamate receptors on glutamatergic nerve terminals and thereby reduces the synaptic release of glutamate (Moran, McFarland et al. 2005). NAC has been recently demonstrated in randomized, double-blind, placebo-controlled studies to be effective for the treatment for bipolar depression and schizophrenia (Berk, Copolov et al. 2008; Berk, Copolov et al. 2008). NAC has also been demonstrated in double-blind, placebo-controlled studies to effectively reduce the symptoms of trichotillomania, a disorder that is considered to be on the OC spectrum and is often comorbid with OCD (Grant, Odlaug et al.

2009). NAC has also demonstrated to be safe without significant side effects in a recent double-blind, placebo-controlled trial in children with autism (Posey, Erickson et al. 2009).

3. **Research Plan:** Provide an orderly scientific description of the study design and research procedures as they directly affect the subjects.

Subjects: Children with OCD will be recruited through the TS/OCD Clinic at the Yale Child Study Center. Inclusion and Exclusion Criteria are listed below.

Intervention: Subjects will be randomized in a ratio of 1:1 to receive treatment with NAC or placebo. NAC (or placebo) will be titrated up to a maximum dose of 2400mg/day over the course of 1 week. Subjects will take a single 600mg tablet twice a day for 1 week, and then increase to two 600mg tablets twice a day for the remainder of the 12 week study. After completion of the study all subjects receiving placebo will be offered NAC treatment for the following 12 weeks.

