The table below indicates the clinical ratings scheduled planned for the trial. If subjects' have significant ADHD, tic, anxiety or depression symptoms at screening, ratings of these symptoms will be followed regularly at study assessments. Subjects will be encouraged to continue outside therapy and will be required to continue all concurrent medications during the course of this trial. Subjects will also be asked about the number of missed doses of medications at each study visit.

Measure	Screening/ Baseline	Week 2	Week 4	Week 8	Week 12
CY-BOCS	X	X	X	X	X
DY-BOCS	X	X	X	X	X
YGTSS	X		X	X	X
ADHD-RS	X		X	X	X
CDI	X		X	X	X
MASC	X		X	X	X
MGH-HPS	X		X	X	X
CGI	X	X	X	X	X
PAERS	X	X	X	X	X
NAC dose	600mg BID	1200 mg BID	1200 mg BID	1200 mg BID	1200 mg BID

3. **Statistical Considerations:** Describe the statistical analyses that support the study design.

We will use the CY-BOCS as our primary outcome measure. Our primary analysis will involve a mixed effects model using weekly CY-BOCS ratings from baseline to 12 weeks with treatment (NAC/placebo) as a fixed factor and time as a within-subject factor. We will adhere to intention-to-treat principles in our analysis. We powered our study to have 80% power to detect a large effect of NAC ($d=0.9$) assuming $\alpha=0.05$. Given a similar variance in the Cy-BOCS scores in previous placebo-controlled trials of pediatric OCD, we would expect this effect size to correspond to a 6.5 point difference in Cy-BOCS between the NAC and placebo groups (POTS

HIC#1004006623

2004). By comparison, the effect size of NAC in the treatment of adults with trichotillomania, using the MGH-HS ($d=1.2$, $N=50$), and in bipolar depression, using the Montgomery-Asberg Depression Rating Scale (MADRS) ($d=0.8$, $N=80$) was considerably larger (Grant, Odlaug et al. 2008).

As a secondary outcome we will examine the safety and tolerability of NAC. Given our sample size of 40 we will have limited power to detect adverse events of low frequency. That being said, assuming that we do not see a side-effect in the placebo group, we will have 80% power to detect NAC related side-effect, if it occurs in one-third of NAC treated subjects. Frequency of side-effects will be measured with the PAERS as discussed in the assessments section.

SECTION VI: RESEARCH INVOLVING DRUGS, DEVICES, BIOLOGICS & PLACEBOS

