In many cases subjects will be screened via telephone. The telephone screen will be used to inform the parent (primary caretaker) about the nature of the study, the duration of the study, number of visits, randomization, etc. The telephone screen will include collecting a brief history to exclude subjects that are unlikely to be eligible. People may not be eligible because of an ongoing medical problem (asthma or pregnancy), presence of an excluded psychiatric diagnosis (see exclusion criteria), or because they are unable to attend scheduled study visits. Interested subjects will be scheduled for a screening visit. The screening visit will occur over one visit. The overall purpose of the screening is to confirm that the subject meets all entry criteria. The first step in the screening visit will be to review the consent form, answer questions about the protocol and to obtain written informed consent. All procedures will be described to the subject in a developmentally appropriate manner.

2. **Inclusion/Exclusion Criteria:** What are the criteria used to determine subject inclusion or exclusion? How will eligibility be determined, and by whom?

Subjects will be well-characterized and must meet selection criteria to be enrolled. The measures used in the baseline assessment will be used by the principal investigators to determine if subjects meet inclusion/exclusion criteria.

Inclusion Criteria:

1. Children aged 8-17 years.
2. Primary diagnosis of OCD.
3. Duration of OCD greater than 6 months.
4. Significant Current OCD symptoms: Current CY-BOCS score greater than or equal to 16.

Exclusion Criteria:

1. Comorbid bipolar disorder, psychotic disorder, substance use disorder, developmental disorder or mental retardation (IQ<70).
2. Recent change (less than 4 weeks) in medications that have potential effects on OCD severity (such as Selective Serotonin Reuptake Inhibitors, clomipramine, naltrexone, lithium, psychostimulants, anxiolytics, or antipsychotics). Medication change is defined

to include either dose changes or medication discontinuation.

3. Asthma requiring medication use within the last 3 months (case reports have linked intravenous NAC administration with asthma exacerbation)
4. Known hypersensitivity or previous anaphylactoid reaction to acetylcysteine or any components in its preparation.
5. Positive pregnancy test or drug screening test.
6. Previous use of N-acetylcysteine (dose greater than 600mg for more than 2 weeks).

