5. **Potential Benefits:** Identify any benefits that may be reasonably expected to result from the research, either to the subject(s) or to society at large. (Payment of subjects is not considered a benefit in this context of the risk benefit assessment.)

Children may benefit from the thorough medical and psychiatric evaluations that they will receive while participating in the study. During the study, subjects will also receive a higher level of evaluation and care than routine treatment. Additionally, subjects may benefit from the study medication.

SECTION X: RESEARCH ALTERNATIVES AND ECONOMIC CONSIDERATIONS

1. **Alternatives:** What other alternatives are available to the study subjects outside of the research?
 - 1) Continuing patient's current medications or therapy, which might include various SSRIs or clomipramine) or cognitive behavioral therapy. Both these interventions have demonstrated efficacy for the treatment of pediatric OCD. All subjects will be recommended to engage in adequate trials of both these interventions before enrolling in the trial.
 - 2) Antipsychotics in addition to SSRIs have shown some benefit for the treatment of refractory OCD in adults. These medications are associated with a significantly greater side effect burden than NAC. Families will be made aware of this additional treatment option prior to enrolling in this study.
 - 3) Since N-Acetylcysteine is FDA approved for use to reduce the extent of liver injury after acetaminophen overdose, the patient's doctor might feel comfortable prescribing it off label to the patient.
2. **Payments for Participation (Economic Considerations):** Describe any payments that will be made to subjects and the conditions for receiving this compensation.
Subjects will be paid a total of \$150 for participation in the study -- \$50 screening assessment, \$25 for each of the 4 follow-up visits. .
3. **Costs for Participation (Economic Considerations):** Clearly describe the subject's costs associated with participation in the research, and the interventions or procedures of the study that will be provided at no cost to subjects.
Families will not be charged for the study medications, clinical assessments, services or laboratory tests directly related to the study. As noted above, some subjects may be seen for a clinical consultation prior to study entry. This clinical consultation will be charged as part of standard of care in the usual manner.

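### The primary mixed model names no interaction, baseline handling, visit or contrast; read literally it dilutes the effect with the pre-treatment visit, and the stated 80% power belongs to a different test

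*Combined protocol and SAP*

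**What the plan says.** The aim in Section V, Statement of Purpose, is confirmatory in wording: "The aim of the study is to determine if N-acetylcysteine is an effective treatment for OCD in children". The test meant to settle it is described once, in Section V, Statistical Considerations, as a mixed model specified thus: "using weekly CY-BOCS ratings from baseline to 12 weeks with treatment (NAC/placebo) as a fixed factor and time as a within-subject factor". The section adds adherence to intention-to-treat. No interaction, baseline covariate or constraint, primary visit, contrast or covariance structure appears there or elsewhere.

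The same section gives the power: "We powered our study to have 80% power to detect a large effect of NAC", with d = 0.9 and alpha = 0.05. It then says "we would expect this effect size to correspond to a 6.5 point difference in Cy-BOCS between the NAC and placebo groups". No time point is attached to the 6.5 points, and no test to the 80%.

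The sample is "Approximately 40 subjects all from Yale" (Targeted Enrollment), and "Subjects will be randomized in a ratio of 1:1 to receive treatment with NAC or placebo" (Research Plan). The sentence calls the ratings weekly. The rating schedule just above it has five CY-BOCS assessments (baseline, weeks 2, 4, 8 and 12), and Section X, Payments for Participation, pays "for each of the 4 follow-up visits".

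**The concern.** With baseline as one of the outcomes and only treatment and time named, the coefficient that answers to treatment is the NAC-placebo difference averaged over every visit, including the one before any drug is taken. That pulls the estimate towards zero. A drug with the planned week-12 effect could be missed, especially if benefit builds over several weeks.

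Several other tests fit the same words: a treatment-by-visit interaction, a treatment-by-time slope, or the week-12 change from baseline. They estimate different things and have different power. While the choice is open it can be made after the data are seen, and the nominal 5% error rate then no longer holds. Baseline as an outcome is not wrong in itself. It works if the model has treatment-by-visit terms and a common baseline mean, but the plan states neither.

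**Working it through.** **Inputs from the protocol.** d = 0.9, difference 6.5 points, alpha 0.05 (taken as two-sided, since one-sided would give 87.5%), 40 subjects at 1:1, so 20 per arm. Implied SD = 6.5/0.9 = 7.22. Five scheduled ratings.

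**Assumptions, not in the protocol.** The 6.5 points is the week-12 difference; complete data; equal variances and compound symmetry; within-subject correlation ρ = 0.3, 0.5 or 0.7; and these differences in points:

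| Onset | Wk 0 | Wk 2 | Wk 4 | Wk 8 | Wk 12 | Mean of five |
|---|---|---|---|---|---|---|
| Linear | 0 | 1.08 | 2.17 | 4.33 | 6.5 | 2.82 |
| Full by week 8 | 0 | 1.63 | 3.25 | 6.5 | 6.5 | 3.58 |
| Full by week 4 | 0 | 3.25 | 6.5 | 6.5 | 6.5 | 4.55 |
| Full from week 2 | 0 | 6.5 | 6.5 | 6.5 | 6.5 | 5.20 |

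**Step 1: reproduce the 80%.** Two-group t-test, 20 per arm: SE = 7.22 × √(2/20) = 2.28; 6.5/2.28 = 2.85; noncentral t on 38 df gives 79.2% (normal approximation 81.2%). This needs no correlation, visit count or onset shape, and the protocol gives none.

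**Step 2: the literal treatment term.** In balanced data under compound symmetry it is the difference in five-visit means. Its SE is 2.28 × √((1+4ρ)/5) = 1.52/1.77/1.99. For linear onset, 2.82 against these SEs gives 44/34/28%.

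**Step 3: the alternatives.** Each SE is 2.28 × √v.
- Treatment-by-visit interaction: noncentral F(4,152), ncp = 10 × Σ(difference − mean)² / (SD² × (1−ρ)).
- Week-12 change from baseline: v = 2(1−ρ), 38 df.
- Baseline-adjusted week-12 contrast: v = 1−ρ², 37 df.
- Baseline-adjusted average of the four post-baseline visits: v = (1+3ρ)/4 − ρ², 37 df.

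| Test | Onset | Power at ρ = 0.3/0.5/0.7 |
|---|---|---|
| Literal treatment term | Linear | 44/34/28% |
| | Full by week 8 | 63/50/42% |
| | Full by week 4 | 83/71/61% |
| | Full from week 2 | 92/82/72% |
| Treatment-by-visit, 4 df | Linear | 56/72/93% |
| | The other three | 66/82/97% |
| Week-12 change from baseline | Any | 65/79/95% |
| Baseline-adjusted week 12 | Any | 83/89/97% |
| Baseline-adjusted post-baseline average | Linear | 68/69/80% |
| | Full from week 2 | over 99% |

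For 80% power the literal term needs 47/63/80 per arm under linear onset and 15/20/25 with full effect from week 2, against 20 planned.

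**Step 4: low correlation.** The entry rule ("Current CY-BOCS score greater than or equal to 16") restricts the baseline range and may lower its correlation with week 12. The baseline-adjusted week-12 contrast still has 81% at ρ = 0.2 and 79% at ρ = 0.

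**Step 5: the favourable reading of 6.5.** If 6.5 points is the averaged coefficient itself, the literal term has 99/95/89%. Because the expected baseline difference is zero, the four later visits must then average 6.5 × 5/4 = 8.1 points, which the plan does not claim.

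**Step 6: choosing after the data.** In 200,000 simulated null trials per correlation, each test alone rejected in 4.9–5.0%. Taking whichever of the literal term and the interaction was significant gave 9.7–9.8%. Adding week-12 change from baseline gave 13.0–13.1%.

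**The case against.** The strongest reply is that the sentence lists the factors of a repeated-measures design and does not say the model is additive. Many readers would take the interaction as included. That may be what was meant, but it is not written, and a 4-df interaction is not the comparison the power figure describes either.

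Second, the literal reading uses five visits although the sentence says weekly. With 13 weekly ratings the averaged term has about 64/47/37% for linear onset, and about 99/94/85% for full effect from week 1. The schedule and the payment terms support five visits, and linear onset falls short on either count.

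Third, an ordinary growth-model reading suits gradual onset. A treatment-by-time slope has 76/88/98% for linear onset, though only 43/56/78% for full effect from week 2. This reading widens the spread between admissible tests.

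Fourth, the sample size is not shown to be wrong. A two-group calculation is a common and often conservative basis for a mixed-model trial, and that it was used here is inferred from the match. Correlation and onset are assumed throughout, and nothing suggests an intention to pick among tests. All of this stands. It limits the claim to an undefined test and estimand, and does not supply the missing definition.

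**Conclusion.** The concern holds, and it must be fixed because this sentence is the only definition of the test that decides the trial's aim. Under the literal reading dilution is certain: with five balanced visits and compound symmetry, the coefficient is four-fifths of the mean post-baseline difference, so at most 5.2 of the planned 6.5 points in the onset shapes examined, and 2.8 if onset is linear. Another covariance structure would weight the visits differently and change the exact figure. Loss of power is not certain: it runs from 28% to 92% over the onset shapes and correlations examined. The stated 80% is sound for a plain two-group comparison at one time point, and about right or conservative for a baseline-adjusted week-12 contrast, but the plan commits to neither. The false-positive figures of about 10% and 13% apply only if the test is chosen after the results are known, which the present wording does not prevent.

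**What to change.** Replace the sentence with one model and one test, before any treatment allocation is opened. Subjects stay blind only until their own 12-week completion, so the first unblinding may come well before the last visit.

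- **Outcomes:** CY-BOCS at weeks 2, 4, 8 and 12, replacing the reference to weekly ratings.
- **Fixed effects:** treatment, categorical visit, treatment-by-visit, and baseline CY-BOCS as covariate; or, equivalently, baseline as an outcome with a common baseline mean.
- **Covariance:** state the within-subject structure.
- **Primary test:** the NAC-placebo difference at week 12, two-sided 0.05.
- **Power:** state that the 6.5 points and the 80% refer to that contrast.

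If the average over post-baseline visits is preferred, name that contrast, leave baseline out of the average, and power it as such. It falls below 80% under linear onset unless the correlation is about 0.7.

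The cost is one paragraph of analysis wording. Baseline CY-BOCS is already collected, so no new data, visits or patients are needed.
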